We hypothesize that SGLT2 inhibition acutely reduces the kidneys demand for oxygen by reducing renal metabolism due to blocked sodium-glucose transportation, and hyperfiltration. We hypothesize that the following changes can be demonstrated after institution of SGLT2 inhibition:

- 1) Lowering of renal artery flow (PC-MRI)
- 2) Lowering of renal cortical perfusion and the ratio of cortical/medullary perfusion (ASL-MRI)
- 3) Better medullary oxygenation: Lowering of the renal medulla T_2^* (BOLD-MRI)
- 4) Decrease of renal oxygen consumption (Q-flow combined with measurement of BOLD in renal artery and vein)

We further hypothesize that autonomic function will improve, and that peripheral blood oxygenation and mitochondrial function will both increase after institution of SGLT2 inhibition.

Study population

Fifteen healthy controls recruited through an advertisement in the local newspapers and 15 persons with type 1 diabetes recruited from Steno Diabetes Center Copenhagen according to the study in-and exclusion criteria.

Inclusion criteria healthy controls:

- Written informed consent must be provided before participation
- Male or female patients > 18 years of age
- Capable of lying in a MR-scanner for two hours

Inclusion criteria persons with type 1 diabetes:

- Written informed consent must be provided before participation
- Male or female patients >18 years of age with a diagnosis of type 1 diabetes (WHO criteria)
- Urinary albumin creatinine ratio (UACR) ≥ 30 mg/g in 2 out of 3 consecutive samples (albuminuria) prior to randomization assessed from electronic laboratory database.
- Capable of lying in a MR-scanner for two hours

Exclusion criteria for all:

- Non-diabetic kidney disease as indicated by medical history and/or laboratory findings
- Renal failure (eGFR<15 ml/min/1.73m²), dialysis or kidney transplantation
- Treatment with beta-blocking medication
- Uncontrolled arrhythmia, 2. or 3. degree AV-block or sick sinus syndrome - assessed from a standard 12-lead electrocardiogram
- Pregnancy or breastfeeding (urine HCG is performed on all fertile women)
- Systolic blood pressure < 90 or > 200 mmHg
- Patients who, in the judgement of the investigator, is incapable of participating
- Exclusion criteria for MRI
 - Claustrophobia
 - Known heart disease

- Known lung disease
- Have had surgery the past six weeks
- Have foreign bodies of metal in the body (e.g. pacemaker, metal plates, metal screws)

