- Exclusion criteria for arterial blood gas sampling (only patients with type 1 diabetes)
 - Absent pulse
 - Raynauds syndrome
 - Buergers Disease (thromboangiitis obliterans)
 - Inadequate or interrupted circulation
 - Anticoagulation treatment
 - Coagulopathies (hypo or hyper coagulable states)
 - Arterial atherosclerosis
 - Insufficient collateral perfusion
 - Partial or full thickness burns over the cannulation site
 - Synthetic arterial or vascular grafts or infection at the proposed site of cannulation

Patients with type 1 diabetes will have the possibility to participate in the study without getting arterial blood gas sampling.

- Healthy control exclusion criteria
 - The subject has a clinically significant abnormal laboratory value and/or clinically significant medical or psychiatric illness.
 - The subject has evidence of clinically significant gastrointestinal, cardiovascular, hepatic, renal, hematological, neoplastic, endocrine, neurological, immunodeficiency, pulmonary, or other disorder or disease.

Patient withdrawal

In case of pregnancy (or desire for pregnancy), female subjects are withdrawn.

Lack of compliance to any of the important study procedures in the discretion of the investigator.

Onset of any disorder considered to compromise the safety by participating in the study.

Unacceptable adverse effects in the discretion of the investigator.

Withdrawal on participants request will be accepted at any time without further justification or consequence to regular treatment at the Steno Diabetes Center Copenhagen.

Withdrawn patients will be replaced by patients recruited in the same manner as described in this protocol.

Recruitment

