Information about civil registration number, phone number, address, diagnosis of T1D and historic levels of urine albumin on outpatients at Steno Diabetes Center Copenhagen is provided by the treatment-responsible doctor and passed on to the study investigator. This information is used for identifying possible participants and recruitment. First contact will be a letter containing the written participant information and the brochure: "Your rights as a participant in biomedical research". In the letter, possible participants will be invited to the information meeting at Steno Diabetes Center Copenhagen. The letter contains telephone number and email for the project-responsible doctor. Non-responders will be followed up by a telephone contact approximately two weeks later. All who wish to participate in the study are invited for an information visit.

Healthy controls will be recruited by advertisement in the local newspapers. In the advertisement, there will be phone number and email of the investigators for contact.

Endpoints

Primary end-point

- Renal oxygenation (T_2^*)

Exploratory end-points

[figure not shown]
- Renal cortical and medullary perfusion
- Renal artery flow
- Renal oxygen consumption
- Peripheral capillary oxygen saturation (SpO_2)
- Arterial blood gasses
 - Arterial blood oxygen partial pressure (PaO_2)

- Arterial blood oxygen saturation (SaO₂)
- PBMC mitochondrial function
- Circulating inflammatory markers
- Baroreflex sensitivity

Study design

Randomized, double blinded, placebo-controlled, cross-over intervention study in patients with type 1 diabetes. Baseline results will be compared to healthy controls.

Figure 1

Flowchart of study design. Healthy controls (CON) will only come for baseline measurements on V1 and V2, except blood gas analysis, which will only be done in randomized patients.

Patients with type 1 diabetes (T1D) will be randomized to SGLT2i or placebo for Visits 1+2 and crossed over for Visits 3+4.

Comparative treatment regimes

Patients in the active arm will be treated with dapagliflozin 50 mg once on site for V2 and once at home on the evening before V3.

Randomization and blinding

Patients will be randomly assigned in a 1:1 ratio to one of the following groups:

- Dapagliflozin for V2 and V3 and placebo for V4 and V5
- Placebo for V2 and V3 and dapagliflozin for V4 and V5

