Clinical chemistry will include measurement of p-HbA1c, p-potassium, p-sodium, p-creatinine, p-albumin, haemoglobin, leucocytes, thrombocytes, haematocrit, p-ALT, p-INR (international normalized ratio), p-lipids (total-, HDL-, and LDL cholesterol and triglycerides). Kidney function (eGFR) will be calculated using the CKD-EPI equation from p-creatinine. Blood samples for clinical chemistry will be analysed on the day of collection and destroyed immediately after.

Peripheral blood monocytes will be purified from blood to examine mitochondrial function at Steno Diabetes Center Copenhagen on V1, V3 and V5. Samples will be analysed on the day of collection and destroyed immediately after.

A research biobank of 4 ml blood per participant will be used for analysis of inflammatory markers. A research biobank means that the samples are frozen, analysed by the end of the study (February 1st 2022) and hereafter destroyed.

Blood gas analysis include arterial blood oxygen partial pressure (PaO₂) and arterial blood oxygen saturation (SaO₂). Blood gas analysis will be performed on site at Rigshospitalet Glostrup on V2 and V4. Samples will be analysed on the day of collection and destroyed immediately after. Blood gas analysis will only be performed on randomized patients.

[figure not shown]
Biobank for unspecified future research

Study participants will be asked if they are willing to donate blood and urine to a biobank for unspecified future research. This biological material will only be used for future research after specific approval from the regional ethical committees.

Study visits

Please note that healthy controls will only participate for the information meeting, V1 and the baseline measurements of V2, except from blood gas analysis. Figure 2 shows an overview of study visits.

Figure 2

Overview of study visits. Patients with type 1 diabetes come for information visit and V1-V5.

Healthy controls come for information visit and baseline measurements of V1 and V2, except blood gas analysis.

BP = blood pressure, MRI = Magnetic resonance imaging, SGLT2i = Sodium-glucose cotransporter-2 inhibitor.

Information meeting (day 0) at Steno Diabetes Center Copenhagen

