Information about the study background, design and aspects of the study will be given by the investigator. After consideration, the participants interested in participating in the study are asked to sign an informed consent form. After signed informed consent, patients will be randomized. See section "Participant information/informed consent" for details on informed consent.

Visit 1 (day 7±6) at Steno Diabetes Center Copenhagen

The study participant will come fasting from the morning and abstinent from medication, alcohol and tobacco use except long-acting insulin, 24 hours before the visit. The study participant is not allowed to do strenuous exercise 24 hours prior to the examination. Visit 1 will take approximately two hours. The following questions, measures and samples are obtained:

- Demographic information, medication and medical history are obtained from electronic medical journal and by interview with the study participant
- Weight and height for calculation of body mass index (BMI)
- Office blood pressure and heart rate
- Routine biochemistry
- Test battery A (baseline)
 - Analysis of mitochondrial function of peripheral blood monocytes
 - Sample kept in research biobank for analysis of inflammatory markers
 - Baroreflex sensitivity assessed by continuous ECG and blood pressure

Visit 2 (day 14±6) at Rigshospitalet Glostrup

The study participant will come fasting from the morning and abstinent from medication, alcohol and tobacco use except long-acting insulin, 24 hours before the visit. The study

participant is not allowed to do strenuous exercise 24 hours prior to the examination. Visit 2 will take approximately eight hours. The following measures will be obtained:

- Test battery B (baseline)
 - MRI session with two measurements of: Renal perfusion, renal artery flow, renal oxygen consumption and T_2^* respectively
 - Peripheral blood oxygen saturation by pulse oximetry
 - Blood gas analysis

A standardized morning meal will be given together with the intervention: Institution of 50 mg SGLT2i/placebo. Exactly three hours after intervention, test battery B will be repeated:

- Test battery B (+3 hours)
 - MRI session with two measurements of: Renal perfusion, renal artery flow, renal oxygen consumption and T_2^* respectively
 - Peripheral blood oxygen saturation by pulse oximetry
 - Blood gas analysis

Then a standardized lunch will be given. Exactly six hours after intervention, test battery B will be repeated:

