- Test battery B (+6 hours)
 - MRI session with two measurements of: Renal perfusion, renal artery flow, renal oxygen consumption and T_2^* respectively
 - Peripheral blood oxygen saturation by pulse oximetry
 - Blood gas analysis

Finally, an optional dinner will be offered. See table 1 for a detailed timetable over visit 2.

Table 1

Time	Patients with type 1 diabetes	Healthy Controls
08:00	Kidney MRI (baseline)	Kidney MRI (baseline)
08:30	Blood oxygen saturation (baseline)	Blood oxygen saturation (baseline)
08:40	Arterial blood sample and analysis (baseline)	-
09:00	Intervention: 50 mg SGLT2i/placebo	-
09:00	Standardized morning meal	Standardized morning meal
12:00	Kidney MRI (+3 hours from intervention)	-
12:30	Blood oxygen saturation (+3 hours)	-
12:40	Arterial blood sample and analysis (+3 hours)	-
13:00	Standardized lunch	-
15:00	Kidney MRI (+6 hours from intervention)	-
15:30	Blood oxygen saturation (+6 hours)	-
15:40	Arterial blood sample and analysis (+6 hours)	-
16:00	Optional dinner	-

Timetable over visit 2

Visit 3 (day 28±6) at Steno Diabetes Center Copenhagen

The study participant will be instructed to take 50 mg dapagliflozin / placebo at the time 21:00 on the evening before visit 3. The study participant will come fasting from the morning and abstinent from medication, alcohol and tobacco use except long-acting insulin, 24 hours before the visit. The study participant is not allowed to do strenuous exercise 24 hours prior to the examination. Visit 3 will take approximately one hour. The following measures and samples are obtained:

- Test battery A (baseline)
 - Analysis of mitochondrial function of peripheral blood monocytes
 - Sample kept in research biobank for analysis of inflammatory markers
 - Baroreflex sensitivity assessed by continuous ECG and blood pressure

Visits 4 (day 42±6) and 5 (day 66±6)

Apart from study medication/placebo, study visits 4 and 5 will be identical to visits 2 and 3 but crossed over in terms of SGLT2i/placebo. Table 2 shows study timetable for randomized patients.

Table 2

Visit	Information visit	V1	V2	V3	V4	V5
Site	SDCC	SDCC	RHG	SDCC	RHG	SDCC
Week	0	1	2	4	6	8
Day	0	7	14	28	42	66
Tolerance (\pm days)		± 6				
General						
Informed consent	x					
Assessment of in- and exclusion criteria	x					
If patient: Randomization	x					
Demography		x				
Concomitant medication		x				
Medical history		x				
Weight and height		x				
BP and heart-rate		x				
Routine biochemistry		x				
Endpoints						

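### Urine HCG is an entry check only: no repeat is scheduled before any dose, so placebo-first women receive their first active dose about 42 days after it

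*Combined protocol and SAP*

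**What the plan says.** - Exclusion criteria for all: "Pregnancy or breastfeeding (urine HCG is performed on all fertile women". No time point is given there.
- Patient withdrawal: "In case of pregnancy (or desire for pregnancy), female subjects are withdrawn". Withdrawn patients are replaced.
- Table 2 marks the assessment of inclusion and exclusion criteria once, at the information visit. That is also the randomization visit: "After signed informed consent, patients will be randomized". The section on informed consent rules out study-specific tests before consent.
- Randomization and blinding gives one of the two sequences as "Placebo for V2 and V3 and dapagliflozin for V4 and V5". The other is the reverse.
- The description of V2 lists MRI, pulse oximetry and blood gases before the dose. The evening dose before V3 is taken at home. For the second period, "study visits 4 and 5 will be identical to visits 2 and 3 but crossed over in terms of SGLT2i/placebo".
- Urine HCG is not named in the text of any visit and has no row of its own in Table 2.

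**The concern.** The sponsor has already decided that pregnant women should not be in this trial: one rule keeps them out at entry and another removes them later. Only the entry rule has a test behind it. After day 0, the withdrawal rule works only if the woman knows of the pregnancy and reports it, and an early pregnancy may be unknown to her.

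The crossover makes the interval unequal. In one sequence the first active dose comes two weeks after the check, and in the other it comes six weeks after. At stake is the possible dosing of an undetected early pregnancy in a woman with type 1 diabetes. Healthy controls receive no drug, so the point does not apply to them.

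**Working it through.** The plan states no figure to reproduce. The check is a reading of the schedule plus subtraction of visit days.

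**Inputs.** Visit days and the tolerance of ±6 days come from the visit headings and Table 2. The home dose is at 21:00 on the evening before the visit, so it falls one day earlier. Table 2 places V5 at both day 66 and week 8 (8 × 7 = day 56), so both are carried. The entry HCG is taken to be on day 0, which is an assumption drawn from the eligibility row.

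| Dosing occasion | Nominal day | Range |
|---|---|---|
| V2, on site | 14 | 8 to 20 |
| Evening before V3, home | 28 − 1 = 27 | 21 to 33 |
| V4, on site | 42 | 36 to 48 |
| Evening before V5, home (V5 on day 66) | 66 − 1 = 65 | 59 to 71 |
| Evening before V5, home (V5 in week 8) | 56 − 1 = 55 | 49 to 61 |

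**Formula.** Gap = dose day − day of the last scheduled check. The minimum uses the earliest dose and the latest check; the maximum uses the latest dose and the earliest check.

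**As written (check on day 0).** Only doses that are active in that sequence are counted.

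- Dapagliflozin-first: V2, 14 − 0 = 14 days (8 to 20); home dose before V3, 27 − 0 = 27 days (21 to 33).
- Placebo-first: V4, 42 − 0 = 42 days (36 to 48); home dose before V5, 65 − 0 = 65 days (59 to 71), or 55 days (49 to 61) if V5 is at week 8.

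The first active dose is therefore 42 − 14 = 28 days further from the check in the placebo-first sequence.

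**With a test on arrival at V2 and V4.**

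- The on-site doses at V2 and V4 have a same-day test, so the gap is 0.
- Home dose before V3: 27 − 14 = 13 days (21 − 20 = 1 to 33 − 8 = 25).
- Home dose before V5: 65 − 42 = 23 days (59 − 48 = 11 to 71 − 36 = 35), or 55 − 42 = 13 days (49 − 48 = 1 to 61 − 36 = 25) if V5 is at week 8.

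The longest nominal gap before an active dose falls from 65 to 23 days, or from 55 to 13 days.

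**Who is affected.** The documents do not give the number of fertile women among the 15 patients. If allocation is balanced, 7 or 8 patients start on placebo, so between 0 and 8 women have the 42-day interval.

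**The case against.** **The entry test is already placed.** A reader might infer, from the absence of an HCG row, that the test is assigned to no visit. The documents do not support that. The test is written into an exclusion criterion, eligibility is assessed at the information visit, and tests must follow consent. Day 0 after consent is the natural reading. This objection stands in full, but it concerns the entry test and leaves the absence of a repeat untouched.

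**Existing safeguards cover the interval.** Adverse events are collected at V2 to V5, a new disorder that compromises safety leads to withdrawal, and women who wish to become pregnant are withdrawn. These lower the chance of a problem. None of them would reveal a pregnancy that the woman does not yet know about.

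**The risk is small.** This is probably true, but it cannot be sized from the documents. They give neither the number of fertile women nor a pregnancy rate, and any rate for all pregnancies would overstate the risk, because recognized ones already lead to withdrawal. They also give no figure for fetal harm from two single doses. A numerical risk for the trial would rest on assumed inputs alone.

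**The same gap might seem to exist for medication.** Table 2 marks concomitant medication at V1 only, so a reader might infer that a newly started anticoagulant would be missed before the V4 arterial samples. The support for this is weak. "Anticoagulation treatment" stands in a list specific to arterial sampling, beside absent pulse, poor collateral perfusion and infection at the puncture site, which can sensibly be judged only at the time of puncture. A patient who meets an item can simply skip the procedure: "Patients with type 1 diabetes will have the possibility to participate in the study without getting arterial blood gas sampling". At most, the protocol could make clear that this list is gone through again at V4. Nor do the documents give a reason for a repeat beta-blocker question at V2 and V4: baroreflex sensitivity, the outcome most plainly linked to such drugs, is measured at V1, V3 and V5.

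**Conclusion.** The point holds in a narrow form. No urine HCG is scheduled after entry, although drug is given on four later occasions and pregnancy requires withdrawal. A protocol followed exactly gives fertile women in the placebo-first sequence their first active dose 42 days (36 to 48) after the only check and their last about 65 days (59 to 71) after it, or 55 (49 to 61) if V5 is at week 8. These figures assume that the entry test is done on day 0 and that visits fall within the stated tolerances.

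It is a low-priority matter of participant safety. It raises no question about bias, the primary endpoint, the sample size or the analysis.

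**What to change.** In Table 2 and in the descriptions of V2 and V4, add a urine HCG for fertile women with type 1 diabetes on arrival, before the 09:00 dose. If it is positive, withdraw the participant under the existing rule. The test belongs at both visits because allocation is concealed, so staff cannot know which period carries the active drug.

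The cost is a dipstick and a few minutes at two existing visits, one row in Table 2, and an occasional cancelled dosing visit. The replacement rule already covers a withdrawal.

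The change shortens the gap but does not remove it. The home doses before V3 and V5 would still have no same-day test, and up to 23 days nominal (11 to 35) would remain before the last active dose, or 13 (1 to 25) if V5 is at week 8.

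As an optional clarification, one sentence could say that the arterial-sampling exclusions are re-checked before puncture at V4.

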Group allocation is concealed to patients as well as investigators. 60 sequentially numbered, opaque, sealed envelopes will be produced by Glostrup Apotek. All persons involved in the conduct of the study are blinded to the randomization code. Randomization codes and envelopes are stored securely at the study site available only for the unblinded site staff in charge of randomizing subjects and dispensing study products to subjects. Sealed codes are marked according to randomization code and distributed according to a pre-distributed order. Should unblinding of a study participant be necessary because of an emergency, a dedicated person at Steno Diabetes Center Copenhagen, not involved in the study, will perform the procedure. Alternatively, the Principal investigator will be able to perform unblinding.

Description of investigational drug and placebo drug

Investigational drug:

Forxiga®, dapagliflozin 10 mg film-coated tablet.

For further information please refer to:

https://www.ema.europa.eu/en/documents/product-information/forxiga-epar-product-information_en.pdf.

Common side effects include hypoglycemia, hypotension, elevated hematocrite, dyslipidemia, back pain, dizziness, skin rash, urinary tract infection, vulvovaginitis and dehydration. Very rare incidents of ketoacidosis have been observed. Side effects have only been observed after use in longer periods and not in single-dose usage, as planned in the present study. A dose of 50 mg has been chosen to achieve optimal efficacy. Once-per-day doses of dapagliflozin for 12 weeks of 2.5 mg, 5 mg, 10 mg, 20 mg and 50 mg have been

demonstrated to be relatively safe across the mentioned doses (20) and no apparent risk is expected from instituting two single-doses of 50 mg dapagliflozin.

Placebo drug:

The composition equals the composition of Forxiga® – just with the active ingredient omitted. Active drug and placebo are similar in appearance and smell.

Drug storage

Forxiga® does not require any special storage conditions

Drug accountability

Patients will be instructed to return all wholly or partially used drugs and study medicine packaging. Drug accountability will be performed at the investigation site.

Study duration

Eight weeks for randomized patients. Two weeks for healthy controls.

Methods

Blood-oxygen-dependent level magnetic resonance imaging

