Mitochondrial function		x		x		x
Inflammatory markers		x		x		x
Baroreflex sensitivity		x		x		x
Kidney MRI			x		x	
Pulse oximetry			x		x	
Blood gas analysis			x		x	
Safety						
Adverse events			x	x	x	x
Study medication						
Drug accountability				x		x

Study timetable for randomized patients. SDCC = Steno Diabetes Center Copenhagen, RHG = Rigshospitalet Glostrup.

Assessment of efficacy

In order to assess the acute physiological response of inhibiting SGLT2 in the proximal tubule, kidney MRI parameters, pulse oximetry and blood gas analysis are obtained before intervention (baseline), three hours after intervention and six hours after intervention. In order to assess the subacute, systemic physiological response, PBMC mitochondrial function, inflammatory markers and baroreflex sensitivity are obtained before intervention (baseline) and 12 hours after intervention. Baseline levels will be compared to those of healthy controls.

Response to dapagliflozin in outcomes in randomized patients will be compared to response to placebo.

Assessment of safety

Definition of SAE, SAR and SUSAR

Serious Adverse Event (SAE):

A Serious Adverse event is an experience that treatment results in any of the following:

- Results in death
- Is life threatening (note: the term life-threatening refers to an event in which the patient was at risk of death at the time of the event; it does not refer to an event which hypothetically might have caused death if it was more severe)
- Requires inpatient hospitalization or results in prolongation of existing hospitalization
- Results in persistent or significant disability/incapacity
- Is a congenital anomaly/birth defect, or
- Is an important medical event that may not result in death, be life-threatening, or require hospitalisation may be considered a serious adverse event when, based upon appropriate medical judgement, they may jeopardise the patient or subject and may require medical or surgical intervention to prevent one of the outcomes listed in this definition.
- Suspicion of transmission of infectious agents must always be considered an SAE.

Serious Adverse Reaction (SAR):

A SAE for which a causal relationship to the study medication is at least possible i.e. a causal relationship is conceivable and cannot be dismissed.

Suspected Unexpected Serious Adverse Reaction (SUSAR):

A SAE which is unexpected and regarded as possibly or probably related to the study medication by the Investigator.

Reporting of SAE SAR and SUSAR

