All characteristics will be presented as means with standard deviation (SD) or if skewed distributions, as medians with interquartile range (IQR). For baseline characteristics, chi-squared test and Fischer's exact test will be used when appropriate. For testing group differences, unpaired student's t-test will be used. For testing the effect of the intervention, linear regressions analyses will be performed adjusting for baseline values of outcome variables. To fulfil the requirement of a normal distribution of the model residuals, determinants will be log-transformed where appropriate. Statistical significance is inferred as a two-tailed P-value < 0.05 . All analyses will be performed in SAS enterprise 7.1.

Data management

Source data identification and source data verification

All clinical study information in this study will be recorded, handled, and stored in a way that allows it accurate reporting, interpretation and verification.

Sponsor/investigator will provide direct access to source data/documents for study related monitoring, audit, IEC/IRB review, and regulatory inspection. Sponsor has made an agreement with the GCP-unit at the University of Copenhagen, Denmark, who will be monitoring the study in accordance with the ICH guidelines for GCP.

Subject data protection

There will be a transfer of information from the doctor responsible for the person in the clinic to the doctor responsible for the research of relevance to study participation and safety in the personal record. All information on study subjects is protected according to law on processing of personal data and the law of health. None of the study related blood samples or data will be stored or analyzed in countries outside the EU.

Data handling

Before initiating the study acceptance from the Danish Data Protection Agency will be obtained. A separate case report form (CRF) will be prepared for each study participant. All health-related matters and sensitive personal data will be handled in accordance with the Danish "act on Processing of Personal Data".

All health-related matters and sensitive personal data (CRF, blood test result etc.) will be depersonalized. All participants will be given a study number referring to their personal information, which will be stored securely and separately. Adequate blinding of all personal data during data processing and publication will be ensured.

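### The stated intervention model leaves out period (and patient) in a 15-patient crossover, which costs precision at any split and lets part of a period shift into the drug estimate when the two orders are uneven

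*Combined protocol and SAP*

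**What the plan says.** **Design.** Under Randomization and blinding, "Patients will be randomly assigned in a 1:1 ratio to one of the following groups", the groups being dapagliflozin then placebo, or placebo then dapagliflozin. Study population sets the number at "15 persons with type 1 diabetes recruited from Steno Diabetes Center Copenhagen". Fifteen is odd, so the closest possible split is 8:7.

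**Allocation list.** "60 sequentially numbered, opaque, sealed envelopes will be produced by Glostrup Apotek", and the sealed codes are "distributed according to a pre-distributed order". The block size, the method of generation and the meaning of the number 60 are not given. Under Patient withdrawal, "Withdrawn patients will be replaced by patients recruited in the same manner as described in this protocol"; the sequence that a replacement receives is not stated.

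**Model.** The Analysis section has one sentence on the drug comparison: "For testing the effect of the intervention, linear regressions analyses will be performed adjusting for baseline values of outcome variables". It mentions no period, sequence or patient term.

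**Baselines.** Table 2 and the visit descriptions give two patterns:
- Kidney MRI, pulse oximetry and blood gas are measured before dosing at both Visit 2 and Visit 4, so each period has its own baseline.
- Under Assessment of efficacy, "PBMC mitochondrial function, inflammatory markers and baroreflex sensitivity are obtained before intervention (baseline) and 12 hours after intervention". Table 2 places these measurements at Visits 1, 3 and 5, so both periods share the Visit 1 baseline.

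**The concern.** In a two-period crossover, anything that moves all patients between the first and second period (season, familiarity with the procedures, calibration, a change in routine care) changes the drug-minus-placebo difference in opposite directions in the two sequences. A period term removes this. Without one, two things happen. The part that does not cancel between the sequences is added to the drug estimate. The part that does cancel stays in the residual and widens the standard error.

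Baseline adjustment is only a partial substitute. If a shift δ moves both the same-day baseline and the post-dose value, and the baseline slope is β, then (1 − β)δ remains. That is the position for MRI, pulse oximetry and blood gas. For the three outcomes with a single Visit 1 baseline, the covariate has the same value in both periods. It drops out of the within-patient contrast and removes none of a shift between Visits 3 and 5.

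**Working it through.** **Inputs from the documents:** 15 patients; 1:1 randomisation to two orders; medullary T2* mean 23, SD 4; planned effect 20%; 80% power; two-sided 5%.

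**Assumptions (not in the documents):** the size of the period shift, the within-patient correlation, and the make-up of the list.

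**1. The plan's own figure.** 0.20 × 23 = 4.6, or 4.6/4 = 1.15 SD. An unpaired two-sample t-test has 80.3% power at 13 per group and 86.0% at 15. The stated 13 is therefore reproduced, as a comparison of two independent groups. It tells us nothing about a period effect.

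**2. Leakage into the estimate.** Without a period term, bias = shift × (n1 − n2)/(n1 + n2), with the sign set by which sequence is larger.

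| Split | Fraction leaking | Bias, shift 2 T2* units | Bias, shift 4.6 |
|---|---|---|---|
| 8:7 | 1/15 = 6.7% | 0.13 | 0.31 |
| 10:5 | 5/15 = 33% | 0.67 | 1.53 |
| 11:4 | 7/15 = 47% | 0.93 | 2.15 |

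The T2* columns assume that the shift moves post-dose values only. For MRI they are therefore upper limits if the same-day baseline moves too.

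**3. How likely is an uneven split?** This depends on the unstated list. A split of 10:5 or worse has probability 30.2% under simple randomisation and 23.3% for the first 15 of an unblocked 30:30 list of 60. A split of 11:4 or worse has 11.8% and 7.2%. A list in small blocks would hold the split at or near 8:7.

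**4. Lost precision at 8:7.** Work in units of the SD of the within-patient difference, with a true effect of 0.778 SD, which gives 80% power in a paired test of 15 with no shift. With a shift of 0.5, the variance of the differences rises from 1 to 1 + 0.5² × (1 − (1/15)²) × 15/14 = 1.267. The standard error is then too large by a factor of √1.267 = 1.125.

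| Split, shift 0.5 SD | Power, no period term | Power, period term |
|---|---|---|
| 8:7 | 68% or 76% by direction | 79% |
| 10:5 | 51% or 88–89% by direction | 75% |

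At 8:7 the real type I error without the term is about 3%: conservative, not inflated. At 10:5 the bias is 0.5 × 5/15 = ±0.17 SD.

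**5. Is period alone enough?** No. The figures in step 4 come from a paired analysis, which already contains the patient. A regression of the kind stated, with the shared baseline and no patient term, was simulated at 8:7 with assumed correlations of 0.3 to 0.7. With period added it gives only about 62–76% power and 1–3% type I error. With period and a within-patient comparison together, simulated type I error is 4.4–5.7% at splits from 8:7 to 11:4 and shifts from 0 to 4.6 units, with bias about 0.

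**6. Price of the term.** The standard error is multiplied by √(15²/(4 n1 n2)): √(225/224) = 1.002 at 8:7 and √(225/200) = 1.061 at 10:5. One residual degree of freedom is used (14 to 13). If there is no shift, power goes from 80% to 79% at 8:7 and to about 75% at 10:5.

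**The case against.** A reader might infer that period and drug effects cannot be separated in this trial. The documents do not support that. Both orders are randomised, so the two are separately estimable unless all 15 patients receive the same order. That has probability 2/2¹⁵ = 0.00006 under simple randomisation and less from a 30:30 list. What is missing is a term in the model.

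A reader might also infer that the 60-envelope list is unbalanced or will run out. That is not shown either. The list may be blocked but undescribed, and 60 may count dose packs rather than patients.

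Other points on this side stand:
- The bias averages zero over randomisation and is 1/15 of the shift at 8:7. Averaged over an unblocked 30:30 list, the paired analysis has type I error of 4.9%, 4.5% and 3.8% for shifts of 0.25, 0.5 and 1 SD. Excess false positives need marked imbalance and a large shift together: in a regression without period or patient terms, 20–31% at 11:4 with a shift of 4.6 units.
- The primary endpoint has a pre-dose baseline in each period. The outcomes without one are all exploratory.
- Drift from assaying on the day of collection applies only to mitochondrial function. Inflammatory-marker samples are frozen and analysed later, and baroreflex sensitivity is a recording. A biological shift between visits could still affect all three.
- At the plan's own effect, a paired analysis has spare power: about 94% at an assumed correlation of 0.3 and 98.5% at 0.5. With a 0.5 SD shift at 8:7 it keeps 87–92% and 96–98%.

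None of this supplies the missing term. It limits how much harm should be claimed.

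**Conclusion.** The point holds as a specification gap that is cheap to close, not as a flaw in the design. The stated regression omits period in an AB/BA crossover of 15 patients. The likely harm is lost precision: at 8:7 with an assumed 0.5 SD shift, power is 4 to 12 percentage points below its 80% starting value, against 1 point lost with the term. Bias is a conditional risk that needs both a real shift and an uneven split. Exposure is greatest for mitochondrial function, inflammatory markers and baroreflex sensitivity, and smaller for the MRI, pulse oximetry and blood gas outcomes.

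The leakage fractions and the cost in standard error follow from the design alone. The power figures rest on an assumed shift and on an effect set to give 80% power. The split probabilities rest on an assumed list. Silence on block size, envelope count and replacements is missing detail, not evidence of imbalance.

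**What to change.** In the Analysis section, state that every dapagliflozin-versus-placebo comparison is a within-patient analysis with treatment and period (first/second) as fixed effects and a patient term. Keep the period-specific baseline as a covariate where one exists. State this before unblinding, so that including period is not a choice made after the data are seen. Do not add period without the patient term, because that alone does not restore nominal error or power. The cost is one or two sentences and one degree of freedom for period.

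As a secondary reporting point, under Randomization and blinding state the block size, what the 60 envelopes correspond to, and which sequence a replacement patient receives. This takes a few lines and needs no change to the design.
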